3.12. Interim Analyses

No interim analysis is planned for this study.

4. STUDY ANALYSES

4.1. Patient Disposition

The number and percentage of patients in the following categories will be summarized for the Safety Analysis Set:

- Patients in each analysis population
- Patients enrolled overall and by country and site
- Patients treated
- Patients who completed treatment
- Patients who discontinued treatment and primary reason for treatment discontinuation and discontinuation due to COVID-19
- Patients who completed study participation
- Patients who stopped study participation and primary reason for stopping study participation and stopping study participation due to COVID-19

Data listings of treatment/study completion information, including the reason for treatment discontinuation and/or stopping study participation will be presented.

4.2. Demographics and Baseline Characteristics

Demographic and baseline characteristics, baseline disease characteristics, baseline efficacy parameters, prior medications (excluding premedication), medical history information, and baseline cardiac structure and function will be summarized.

4.2.1. Demographics and Baseline Characteristics

Age, height, weight, and body mass index (BMI) will be summarized using descriptive statistics. Sex, race, ethnicity, and country will be summarized using counts and percentages.

All demographic and baseline characteristic data will be included in by-patient data listings.

4.2.2. Baseline Disease Characteristics

The following baseline disease characteristics will be summarized descriptively:

- Age at hATTR amyloidosis symptom onset
- Age at diagnosis with hATTR amyloidosis
- Genotype
- Liver Transplant History
 - Age at Liver Transplant
 - Type of liver transplant
 - Time from liver transplant to first dose of patisiran

- NYHA classification
- NT-proBNP

All baseline disease characteristic data will be included in by-patient data listings.

4.2.3. Baseline Efficacy Parameters

Baseline values of continuous efficacy parameters (TTR, NIS [total score and component scores], Norfolk QoL-DN, R-ODS, COMPASS-31, and mBMI) will be summarized using descriptive summary statistics. The frequency and percentage of patients in each category for baseline KPS (70, 80, 90, 100) and baseline FAP stage (0, I, II, III) will be tabulated.

A shift table will be used to summarize the historical change in polyneuropathy disability (PND) score; this table will summarize the earliest PND score (most recent PND score prior to OLT or first post-OLT PND score) versus the baseline PND score.

All baseline efficacy parameters will be included in by-patient data listings.

4.2.4. Medical History

Medical history will be tabulated by MedDRA system organ class (SOC), high level term (HLT) and preferred term (PT). A patient contributes only once to the count for a given condition (overall, by SOC, by HLT, or by PT).

Medical history including prior surgeries will be included in a by-patient data listing. Baseline cardiac medical history will also be included in a by-patient data listing.

4.2.5. Prior Medications

Prior Medications will be defined as those medications that were initiated prior to first patisiran administration and are not considered premedications for patisiran administration. For medications with partial start or stop dates: the first day/month will be imputed for start date, and the last day/month will be imputed for stop date. For medications with a completely missing start date, the medications will be considered as started prior to the first dose of study drug; medications will be classified as prior, concomitant or both depending on the medication stop dates. For medications with a completely missing stop date, the earlier of the data cut-off date or the end of study date will be imputed.

Prior medications will be coded using the WHO Drug Dictionary (September 2018 or later). Results will be tabulated by ATC and PT; patients will only count once for each ATC or PT if they have multiple medications with the same ATC or PT.

Prior medications will be included in a by-patient data listing.

4.2.6. Baseline Cardiac Structure and Function

Baseline cardiac structure and function will be assessed through echocardiograms. Twelve (12)-lead electrocardiograms will also be performed. Baseline echocardiogram parameters (including wall thickness, ejection fraction, and other echo parameters) and baseline 12-lead electrocardiogram parameters in triplicate (including rhythm, ventricular rate, RR interval, PR interval, QRS duration, QT interval [uncorrected], QTcB, and QTcF) will be summarized using descriptive summary statistics and will also be included in by-patient data listings.

4.3. Pharmacokinetic Evaluations

Pharmacokinetic analyses will be performed for ALN-18328 and 2 novel lipids (DLin-MC3-DMA and PEG2000-C-DMG) using noncompartmental analysis methods. PK analyses will be based on the Pharmacokinetic Analysis Set. Summaries will be provided for each scheduled time point. PK data will be included in by-patient data listings.

The following PK parameters will be estimated for each subject, as appropriate and if data permits: maximum plasma concentration (C_{max}), time to maximum plasma concentration (t_{max}), terminal elimination half-life ($t_{1/2\beta}$), area under the concentration-time curve during a dosing interval ($AUC\tau$), systemic clearance at steady state (CL_{ss}), and apparent volume of distribution at steady state (V_{ss}), and accumulation ratio for PK exposure parameters (R_{ac}). Additional PK parameters may be calculated, if deemed necessary. The PK parameters will be summarized using descriptive statistics.

4.4. Efficacy Analyses

Primary efficacy analysis will be based on the Safety Analysis Set. Secondary and exploratory efficacy analyses will be based on the Per Protocol Analysis Set. Summaries will be provided for each scheduled time point. Efficacy data will be included in by-patient data listings.

4.4.1. Primary Endpoint

The primary endpoint is the average TTR percent reduction from baseline across Month 6 and Month 12.

For all analyses of post-baseline TTR data, only post-baseline TTR assessments collected within 24 days (inclusive) after receiving a complete dose of patisiran (see Section 4.5.1) will be summarized.

The median TTR percent reduction from baseline along with the 2-sided 95% distribution-free CI will be provided. The p-value for the TTR percent reduction from baseline will be obtained using the Wilcoxon signed-rank test.

A summary table will present the observed value, change from baseline, and percent change from baseline in serum TTR by visit. A boxplot will also present the percent change from baseline by visit.

Serum TTR data will be included in a by-patient listing.

4.4.2. Secondary Endpoints

4.4.2.1. NIS

Neurologic impairment will be assessed by NIS. The total NIS score is the sum of NIS-W, NIS-R, and NIS-S. Scoring algorithms for NIS score are included in Section 7.1.1. LOCF will be used for imputation for the missing NIS assessments at Month 12 as described in Section 3.10.1.

NIS absolute values and changes from baseline in the composite (total NIS score) and component scores (NIS-W, NIS-R, NIS-S) will be summarized by visit.

Observed NIS scores will be included in a by-patient listing.

4.4.2.2. Norfolk QoL-DN and R-ODS

Patient reported quality of life and disease burden will be assessed by summary statistics for the Norfolk QoL-DN total score and R-ODS. Scoring algorithms for the Norfolk QoL-DN and R-ODS are included in Section 7.1.2 and Section 7.1.3 respectively. LOCF will be used for imputation for the missing Norfolk QoL-DN and R-ODS assessments at Month 12 as described in Section 3.10.1.

The absolute values and changes from baseline in these measures will be summarized descriptively by visit. Continuous statistical summaries of each Norfolk QoL-DN domain score will also be provided.

Observed Norfolk QoL-DN and R-ODS scores will be included in by-patient listings.

4.4.2.3. COMPASS-31

Patient reported autonomic neuropathy symptoms will be assessed by the COMPASS-31 total score. Scoring algorithms for COMPASS-31 are included in Section 7.1.4.

The observed values and changes from baseline in COMPASS-31 will be summarized descriptively by visit. Continuous statistical summaries of each COMPASS-31 domain score will also be provided.

The COMPASS-31 total score will be analyzed using a mixed-effects model for repeated measures (MMRM), which makes use of fully and partially observed data sequences from individual patients by estimating the covariance between data from different time points. The MMRM will be implemented using an unstructured approach to modeling both the treatment-by-time means and the (co)variances, leading to what is essentially a multivariate normal model wherein treatment group means at the primary time point are adjusted to reflect both the actually observed data and the projected outcomes from the patients with missing data (Mallinckrodt et al, 2008). MMRM also assumes data are missing at random (MAR).

In the MMRM model, the outcome variable is the change from baseline in COMPASS-31 total score; the model includes baseline COMPASS-31 total score as a continuous covariate and visit (Month 6 or Month 12) as a fixed effect term. Least-squares (LS) mean estimates, SEMs and 95% CIs at Month 6 and Month 12 will be presented. An unstructured covariance structure will be used to model the within-patient errors. If the model fails to converge, the compound symmetry covariance structure will be used. The Satterthwaite approximation will be used to estimate the degrees of freedom.

Observed COMPASS-31 scores will be included in a by-patient listing.

4.4.2.4. mBMI

mBMI is calculated as BMI (kg/m^2) multiplied by albumin (g/L). LOCF will be used for imputation for the missing mBMI assessments as described in Section 3.10.1.

Descriptive statistics will be provided for absolute values and changes from baseline in nutritional status (mBMI).

Observed mBMI values will be presented in a by-patient listing.

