1.2. Study Design

1.2.1. Synopsis of Study Design

Study 008 is a global Phase 3b open-label study designed to evaluate the safety, efficacy, and PK of patisiran in patients with hATTR amyloidosis with disease progression after liver transplant. All eligible patients will be administered open-label patisiran.

The open-label design is supported by previous studies, including a pivotal Phase 3 double-blind, placebo-controlled study (ALN-TTR02-004; hereinafter referred to as the APOLLO study). The clinical benefits seen in the APOLLO study were observed in association with an 80% reduction of TTR with patisiran within 10 to 14 days after a single dose, which was maintained over the duration of the 18-month study compared to no change with placebo. The primary efficacy endpoint in the current study, TTR reduction, is an objective measurement and not susceptible to bias of clinical study center staff or study patients and therefore does not require a blinded placebo group for accurate interpretation.

Consented eligible patients enrolled in this study will receive 0.3 mg/kg patisiran IV once every 3 weeks for 12 months. Dosing is based on actual body weight. For patients weighing 100 kg or more, patisiran will be administered at a total dose of 30 mg IV once every 3 weeks. Eligibility for this study will be confirmed before administration of the first dose on Day 1.

Safety will be assessed throughout the study. Patients will return to the clinical site for safety evaluations at Week 12, Month 6, and Month 12. Patients will be continually assessed throughout the study for adverse events (AEs). Unscheduled visits for study assessments may occur if deemed necessary by the study personnel.

Efficacy assessments will be performed at baseline, 6 and 12 months.

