5. CHANGES TO PLANNED ANALYSES

Modifications to planned analysis specifications from the protocol are documented below:

Section	Description	Rationale
Section 2.1	Per Protocol Analysis Set was added.	The Per Protocol Analysis Set was added to support primary analyses of estimating treatment effects of secondary and exploratory efficacy endpoints in patients who did not miss or missed less than or equal to 2 doses of patisiran due to COVID-19.
Section 4.4.1	The Hodges-Lehmann method's estimates of median TTR percent reduction and its 2-sided 95% CI were modified to standard median TTR percent reduction and its 2-sided 95% distribution-free CI, respectively.	The reason of the change is because there is no available SAS procedure in most current SAS version for one-sample Hodges-Lehmann method. Based on simulations, the estimated medians and the 2-sided 95% CIs are similar for the two methods.
Section 3.10.1 Section 4.4.2.1 Section 4.4.2.2 Section 4.4.2.4	The primary analysis for the NIS, Norfolk QOL-DN, R-ODS and mBMI efficacy endpoints was updated to use LOCF to impute missing post-baseline values.	The changes from baseline in NIS, Norfolk QOL-DN and R-ODS assessments between Months 9 and 18 and mBMI assessments between Months 3 and 18 were relatively stable in the patisiran arm of the APOLLO study. Thus, the LOCF method was adopted to account for the potential missingness (including missingness related to COVID-19) in NIS, Norfolk QOL-DN, R-ODS and mBMI efficacy endpoints during this study.
Section 4.4.2.3	The primary analysis for the COMPASS-31 efficacy endpoint was changed to MMRM.	The changes from baseline in COMPASS-31 total score showed improvement from Month 9 to Month 18 in the patisiran arm of the APOLLO study. Thus, the MMRM method was adopted to account for potential missingness (including missingness related to COVID-19) in COMPASS-31 total score, which assumes data are Missing at Random (MAR).

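### The single-arm COMPASS-31 MMRM adjusts for baseline but omits baseline sampling variation, so its 95% CIs are too narrow for the population mean change

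*SAP*

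**What the plan says.** The study has one arm: "All eligible patients will be administered open-label patisiran" (SAP 1.2.1). For COMPASS-31, SAP 4.4.2.3 specifies an MMRM in which "the outcome variable is the change from baseline in COMPASS-31 total score" and "the model includes baseline COMPASS-31 total score as a continuous covariate and visit (Month 6 or Month 12) as a fixed effect term". There is one baseline slope common to both visits and no treatment term. "An unstructured covariance structure will be used to model the within-patient errors", with compound symmetry if the model does not converge. "The Satterthwaite approximation will be used to estimate the degrees of freedom". The output is stated as: "Least-squares (LS) mean estimates, SEMs and 95% CIs at Month 6 and Month 12 will be presented".

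SAP section 5 gives this model its status: "The primary analysis for the COMPASS-31 efficacy endpoint was changed to MMRM". The reason given there is missing data under MAR.

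The SAP does not say at which baseline value the LS means are evaluated, whether the interval is meant to be conditional on the observed baselines, or whether baseline variation enters the SE. SAP 4.4.2.3 also asks for observed values and changes by visit. SAP 3.2 makes every non-primary summary descriptive.

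**The concern.** In a two-arm trial the reported quantity is a difference. The mean baseline largely cancels, and adjustment makes the estimate more precise. In one arm the mean change itself is reported, and nothing cancels.

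With complete data, the LS mean at the sample mean baseline is the plain mean change. Adjustment therefore leaves the estimate as variable as before but attaches a smaller SE to it. The report could show the same mean change twice: once in the by-visit summary with the ordinary SEM, and once from the primary model with a smaller SEM and a CI built on it.

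COMPASS-31 is the only secondary endpoint for which SAP 4.4.2 specifies a confidence interval. With no comparator and at most about 20 patients, that interval is the main statement of uncertainty about the change in autonomic symptoms.

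**Working it through.** **The plan's own figure.** The only precision figure in the documents is for TTR (SAP 3.1): SD 18%, n = 16, half-width about 10%. It reproduces: t(0.975, 15) × 18/√16 = 9.59 (8.82 with the normal quantile), and 16/0.8 = 20 enrolled. This supplies n = 16 to 20. No precision is stated for COMPASS-31.

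**Assumed inputs, not in the documents.** Correlation ρ between baseline and follow-up score: 0.4 to 0.9. Ratio k of follow-up SD to baseline SD: 0.8, 1.0, 1.2.

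**Formulas** (baseline SD σ_B):
- slope of change on baseline: β = ρk − 1
- residual variance: σ_res² = k²(1 − ρ²)σ_B²
- variance the model reports for the LS mean: σ_res²/n
- sampling variance of the same estimate: (σ_res² + β²σ_B²)/n
- large-sample coverage of a nominal 95% CI: 2Φ(1.96√R) − 1, where R = σ_res²/(σ_res² + β²σ_B²)

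For k = 1, R reduces to (1 + ρ)/2. Example with ρ = 0.5: σ_res² = 0.75σ_B² and β² = 0.25, so R = 0.75, √R = 0.866 and coverage is 91.0%. The correct SE is 1/0.866 = 1.15 times the reported one.

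| ρ | R (k = 1) | Correct SE / model SE (k = 1) | Coverage, k = 1 | Coverage, k = 0.8 | Coverage, k = 1.2 |
|---|---|---|---|---|---|
| 0.4 | 0.70 | 1.20 | 89.9% | 84.9% | 92.4% |
| 0.5 | 0.75 | 1.15 | 91.0% | 86.2% | 93.3% |
| 0.6 | 0.80 | 1.12 | 92.0% | 87.2% | 94.0% |
| 0.7 | 0.85 | 1.08 | 92.9% | 88.0% | 94.6% |
| 0.8 | 0.90 | 1.05 | 93.7% | 88.3% | 95.0% |
| 0.9 | 0.95 | 1.03 | 94.4% | 87.4% | 94.7% |

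**Small-sample check of the SAP's model.** The MMRM was simulated with REML, unstructured covariance, a common baseline slope and Satterthwaite df, with 2,500 runs per setting (Monte Carlo error about 0.5 points). Settings were n = 16, n = 20, and n = 20 with 20% of Month 12 missing, all with equal SDs. Coverage over both visits was:
- ρ = 0.5: 90.9–92.2%
- ρ = 0.6: 91.8–93.0%
- ρ = 0.7: 92.0–93.5%
- ρ = 0.8: 93.4–94.2%
- ρ = 0.9: 94.2–95.1%

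At n = 20, ρ = 0.5 and 20% missing, the model SE was 0.207 against an empirical SD of 0.237 (in baseline SDs).

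**Other intervals.** In a complete-data simulation of the baseline-adjusted mean change (100,000 runs, n = 16 and 20, all ρ and k above):
- default LS-mean CI, for the mean change at the observed mean baseline: 94.8–95.1%
- plain t interval on the observed mean change: 94.8–95.2%
- LS-mean CI with β²s_B²/n added to the variance: 95.3–95.8%

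Modelling baseline as a response gave 94.8% (ρ = 0.5) and 94.6% (ρ = 0.7) at n = 20 with 20% of Month 12 missing. That rests on 500 fits per setting, with a Monte Carlo error of about 1 point.

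**The case against.** **The interval is valid for another target.** For patients whose mean baseline equals the observed one, coverage is about 95%. This stands: too narrow is a statement about the population mean change. But the SAP never declares the conditional target. Its objective is the effect in the patient population, and its reason for the MMRM is missing data.

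**Nothing is decided on this interval.** This also stands. SAP 3.2 makes the analysis descriptive, and SAP 3.5 and 3.6 specify a single hypothesis, on TTR. A reader might infer that the narrow interval could yield a false claim of change by excluding zero. The documents attach no test or success criterion to COMPASS-31, so that reading goes too far. The observed by-visit summaries also let a reader see the unadjusted change and its SEM. They cover observed cases only and do not correct the model's CI.

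**One coverage figure cannot be read from the plan.** A reader might settle on 92–93%. That needs a correlation of about 0.6 to 0.7 and equal SDs, and the documents give neither. The loss could be negligible, or larger.

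**The comparative wording is background.** The phrase "wherein treatment group means at the primary time point are adjusted to reflect both the actually observed data" might suggest that a two-arm model is to be fitted. It describes MMRM in general; the model specified in the next paragraph contains only baseline and visit. The problem is the SE of a single-arm LS mean, whatever that wording says.

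**Conclusion.** The point holds as an understatement of uncertainty. Its direction is certain whenever the slope of change on baseline is not zero, the LS mean is evaluated at the sample mean baseline, and the target is the population mean change.

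Its size is conditional. With equal SDs and n = 16 to 20, coverage is about 91–94% for correlations of 0.5 to 0.8. Over SD ratios of 0.8 to 1.2 and correlations of 0.4 to 0.9, it is about 85–95%. All of these SDs and correlations are assumptions.

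With complete data the point estimate is unaffected. What is wrong is the stated precision of one descriptive secondary endpoint. It is worth correcting because the correction is short.

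**What to change.** Amend SAP 4.4.2.3 in one of two ways.

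1. **Keep the model and correct the variance.** State the baseline value at which the LS means are evaluated, and add slope² × s_B²/n to the LS-mean variance before forming the SEM and CI. This is the smaller edit. Coverage was about 95–96%, checked with complete data.

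2. **Make baseline a response.** Model baseline, Month 6 and Month 12 scores with visit means only, an unstructured 3×3 covariance and Satterthwaite df. Report the Month 6 minus baseline and Month 12 minus baseline contrasts with 95% CIs. Two consequences need text:
   - The compound-symmetry fallback would force equal variances and one common correlation across baseline and follow-up. Replace it with a structure that allows visit-specific variances, such as heterogeneous compound symmetry.
   - Patients with a baseline but no post-baseline score could now enter the model, whereas a change-score model excludes them. State whether they are included.

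   This option also replaces the common baseline slope with visit-specific relationships, so the treatment of missing Month 12 scores is similar to the present one but not identical.

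If the sponsor does want an interval conditional on the observed baselines, the SAP should say so and the table should be labelled accordingly.

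The cost is SAP wording, a few lines of code and a wider reported CI: about 3–15% with equal SDs (correlations 0.9 down to 0.5). It is more if the follow-up SD is smaller than the baseline SD; at a ratio of 0.8 the factor is 1/0.80 to 1/0.733, or 25–36%.

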4.4.3. Exploratory Endpoints

4.4.3.1. FAP stage and PND score

Changes in ambulation will be evaluated through the PND score and FAP stage. The actual PND score or FAP stage and their comparisons with baseline (ie, improved, no change or worsened) will be summarized by visit. Tables for shift in PND score or FAP stage from baseline to worst post-baseline assessment will also be provided.

FAP stage and PND score will be presented in separate by-patient listings.

4.4.3.2. KPS

Functional impairment is assessed by the KPS scale. The actual KPS score and changes from baseline will be summarized by visit. A listing for the KPS score by patient will also be provided.

4.5. Safety Analyses

Safety analyses will be based on the Safety Analysis Set and will consist of study drug exposure, adverse events (AEs), clinical laboratory assessments, vital signs and physical examinations, liver allograft status, premedications, prior and concomitant medications.

4.5.1. Study Drug Exposure

For the purpose of calculating the duration of study drug exposure, the last date of exposure to patisiran is defined as the earliest day of the following dates:

- Last dose date + 20 days
- Analysis cutoff date
- End of study date

Duration of exposure in months is defined as (the last date of exposure to study drug – date of the first dose +1)/30.4375.

Duration of drug exposure in months, the total number of doses received, duration of infusion (per infusion), amount of patisiran received (per infusion and in total), number and percentage of patients with any missed doses and infusion interruptions, number of missed doses, and number of infusion interruptions for any reason as well as due to an infusion related reaction (IRR) will be summarized.

Study drug exposure by visit, including duration of infusion and total infusion volume administered will be summarized.

The numbers and percentages of patients with complete and partial dose administrations will also be summarized. Complete and partial administration is defined as follows:

- Complete: $\geq 80\%$ (≥ 160 mL) of the planned infusion volume (200 mL)
- Partial: $>0\%$ to $<80\%$ (>0 to <160 mL) of the planned infusion volume (200 mL).

Dosing information including phone contact information for home infusions will be included in a by-patient data listing.

